3.1.1. Intercurrent Events

The following events will be considered intercurrent events for the MIT-E study:

- Use of rescue medications for seizures
- Emergency room visits and hospitalizations
- Changes in anti-seizure medications, except weight-based adjustments
- Discontinuations due to withdrawal, noncompliance, and death during the double-blind period.

Subjects with changes in anti-seizure medications and subjects who discontinued from the study will be excluded from the Per Protocol population and will be assessed in separate sensitivity analyses.

Sensitivity analyses will not be performed for subjects that have use of rescue medications, visits to the emergency room, or hospitalizations, as these events will not have long term impact on the effectiveness of study treatment.

Sensitivity analysis performed regarding these intercurrent events are described in Section [5.1.3](#).

3.2. General Considerations

For continuous variables, median, mean, standard deviation, minimum, maximum, and number of subjects with non-missing data will be provided for each treatment group, and for overall treatment group for assessment prior to randomization. For categorical variables, the number (percent) of subjects in each category will be provided.

Day 1 is defined as first dose date relative to double-blind period. Relative days after day 1 are calculated as: assessment date - first dose date + 1. Relative days prior to day 1 are calculated as assessment date - first dose day.

All study days will be calculated as relative to the first dose day of double-blind period.

All analyses will be based on observed data only, and no missing values will be imputed except specifically indicated, for example, components of a date.

Measurements collected from unscheduled visits, or repeated assessments will be included in the listings only unless otherwise specified. Source data for the summary tables and statistical analyses will be presented as subject data listings.

In general, statistical inferential statistics will only be performed for the double-blind period using 2-sided α of 0.05 level of significance. The descriptive summaries will be presented by treatment groups (placebo, vatiquinone) and in total (where applicable) during double-blind period for both efficacy and safety endpoints. In addition, on-vatiquinone experience from both double-blind and open-label extension period will be combined and summarized for safety endpoints. In On-vatiquinone summaries, baseline for subjects on placebo in the double-blind period will be the last observation prior to the first vatiquinone dose.

3.3. Data Safety Monitoring Board

A Data Safety Monitoring Board (DSMB) has been set up for this study. The primary responsibility of the DSMB is to protect the safety and welfare of subjects participating in this clinical trial.

Periodic DSMB meetings are planned to monitor subject safety. Unblinded outputs on subject disposition, demographic and baseline characteristic, efficacy, safety, and PK will be reviewed by DSMB members. Details are provided in the DSMB charter and DSMB SAP.

3.4. Interim Analyses

No formal interim analyses are planned for this study.

However, there will be 2 database locks for this study. The first database lock (soft lock) will occur when all subjects complete the double-blind treatment (Week 24). The study will be unblinded after soft lock. The final database lock will occur when all subjects have completed open-label treatment period. The subjects and investigators will remain blinded to the treatment assignment until the final data base lock.

3.5. Baseline

For safety endpoints, baseline for double-blind period and open-label period will be defined as the last measurement prior to or on the date of first dose date.

For efficacy endpoints during double-blind period, baseline is defined as the 28 days prior to randomization. Baseline definition for the seizure frequency, disease-related hospitalization days, and occurrence/recurrence of status epilepticus per 28 days will be calculated as the number of seizures, hospitalization days, and status epilepticus, respectively, during the run-in period, divided by the number of days in the run-in period, and multiplied by 28. Only “valid days” will be used in the calculation of seizure frequency per 28 days. A “valid day” is defined as a day where seizure counts information is present.

For summary, based on on-vatiquinone period, the baseline will be defined as the last measurement prior to the first dose of vatiquinone. ie, the last assessment prior to first dose in subjects with treatment sequence vatiquinone/vatiquinone, or the last assessment prior to first open-label vatiquinone in subjects with treatment sequence placebo/vatiquinone. For subjects who are randomized to placebo group in double-blind period and enter into the open-label period, all assessments conducted on the day they take last dose of double-blind period drug will be considered as baseline for the on-vatiquinone period.

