Abbreviations: AE, adverse event; ALT, alanine aminotransferase; AST, aspartate aminotransferase; CBC, complete blood count; COVID-19, coronavirus disease 2019; ECG, electrocardiogram; EEG, electroencephalogram; eCRF, electronic case report form; PedsQL, Pediatric Quality of Life Inventory™; PK, pharmacokinetics; SAE, serious adverse event; w/diffs, with differentials

^a Screening will be conducted and completed in a maximum of 42 days (up to 14 days Screening and 28 days Run-in period) prior to the Baseline Visit. Before the Run-in period subjects will be trained in diary completion. The Run-in phase and initiation of the seizure diary completed during this phase of the study, will contain a minimum of 28 consecutive days of seizure data collected prior to the Baseline Visit. Ideally the subject will be instructed to start entering diary information the day after Screening, so that the requisite number of days can be collected prior to the Baseline Visit. Laboratory tests from within 30 days of Screening are acceptable for entry to the study.

^b The follow-up visit will be conducted via telephone 30 days (±7 days) after last dose or termination visit.

^c Telephone call only.

^d ECG measurement will be performed at 4 hours postdose during each visit, time-matched to PK blood collection. Electrocardiogram should be performed approximately within 10 minutes preceding the 4-hour PK blood collection.

^e EEG for epilepsy confirmation if historical EEG up to 6 months prior to screening for confirmation of epilepsy is not provided.

^f Height will only be collected at the Screening Visit; all subsequent visits will collect weight and oxygen saturation only. Any change in weight of ≥10% from Baseline should result in dose adjustment. Weights ending in decimals ≥0.5 should be rounded up to the next whole number for dosing calculation.

^g Female subjects of childbearing potential must have a negative serum pregnancy test at Screening and a negative urine pregnancy test at all other indicated timepoints. If a subject cannot perform a urine pregnancy test at any timepoint, a serum pregnancy test should be performed. At-home urine pregnancy test kits will be provided; subjects will be required to perform the test at home 30 days after the last dose of study drug and self-report the results via telephone.

^h ALT, AST, and creatinine are the only chemistries required at the Screening Visit.

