ⁱ Blood will be drawn for PK assessment predose and 1, 3, 4, and 8 hours postdose (prior to the next dose of vatiquinone) at Baseline and Week 24, and only 4 hours postdose at Weeks 48 and 72. For subjects weighing less than 10 kg, PK blood draw can be reduced to 2 timepoints per visit at the Baseline and Week 24 visits. Recommended timepoints are 0 (predose) hour and 4 hours postdose.

^j During the Screening Visit, the subject's caregiver will be trained on how to capture information in the seizure diary and hospital admissions log.

^k Serious adverse events will be assessed from the Screening Visit through 30 days following the last dose of study drug should be reported via the SAE report form to PTC within 24 hours of becoming aware of the event(s). In addition, the AE portion of the eCRF must also be completed.

^l The follow-up contact will be by telephone and should be completed 30 days (± 7 days) post last study drug administration or termination visit, whichever is later. Adverse events and SAEs will be followed until resolution or until they have normalized. At the investigator's discretion an office visit and additional tests may be conducted in order to ensure proper follow-up of an AE/SAE.

^m First dose for the placebo-controlled phase of the study will be taken the same day as the Baseline Visit. Study drug will be dispensed during the Baseline Visit and at each subsequent in-person visit. Drug may be delivered via delivery service if needed.

ⁿ From Week 24 onwards, vatiquinone will be dispensed to all subjects entering the long-term extension phase. Vatiquinone will be dispensed after completing the Week 24 assessments. The subjects will enter the open-label phase of the study and receive vatiquinone for the dose after the visit.

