7.1.2.1. Baseline Visit/Randomization

The following assessments and procedures will be performed at Baseline Visit:

1. Review of all previous screening testing performed on the subject
2. 12-lead ECG at 4 hours postdose time-matched to pharmacokinetic (PK) blood collection; ECG should be performed approximately within 10 minutes preceding the 4-hour PK blood collection
3. Weight and oxygen saturation
4. Physical Examination including vital signs
5. Urine or serum pregnancy test: WOCBP must have a negative urine or serum pregnancy test (see Section 7.4.3)
6. Laboratory assessments for hematology, coagulation, serum chemistry, and urinalysis (see Section 7.4.2)
7. Randomization
8. The study drug will be administered at Baseline Visit by site staff or caregiver will be trained to administer the first dose on site
9. Blood samples drawn for PK analysis predose and 1, 3, 4, and 8 hours postdose (prior to the next dose of vatiquinone). For subjects weighing less than 10 kg, PK blood draw can be reduced to 2 timepoints per visit. Recommended timepoints are 0 (predose) hour and 4 hours postdose.
10. AE/SAE assessment
11. Concomitant medications assessment
12. Review of seizure diary
13. Calculation of total hospital admissions and total hospital days for disease-related issues from the time of the Screening Visit
14. CarerQoL-7D questionnaire
15. PedsQL questionnaire
16. Dispense study drug

During the Baseline Visit, study medication will be dispensed to the subject according to the randomization. First dose for the study drug will be taken the same day as Baseline Visit and PK samples collected during the Baseline Visit.

Subjects randomized to the treatment arm will be required to take study drug in a formulation mixed with sesame oil NF. Subjects in the placebo group will receive sesame oil with a colorant, which will have similar appearance and consistency as vatiquinone. In case the subject has a gastrostomy tube or nasogastric tube (G-tube or nasogastric tube) installed, vatiquinone or placebo will be administered using an amber oral dispenser into the G-tube with liquid food. If the subject is able to swallow, vatiquinone or placebo can be administered using an amber oral dispenser along with food.

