1.3.4.1. Clinical Variables

- All AEs and SAEs
- Drug-related SAEs
- Drug-related AEs

1.3.4.2. Physical Examination, Vital Signs, 12-lead Electrocardiogram (ECG) and Electroencephalogram (EEG)

- Vital signs include height, weight, temperature, respiratory rate, systolic blood pressure, diastolic blood pressure, heart rate and oxygen saturation.
- Physical examination includes general appearance, skin, head, eyes, ears, nose, throat, neck (including thyroid), lymph nodes, chest, heart, abdomen, and extremities.

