6.5. Electrocardiogram (ECG)/Electroencephalogram (EEG)

ECG results and change from baseline results (heart rate, PR interval, RR interval, QRS interval, QTc interval) along with ECG interpretations will be summarized at each visit by each assessment timepoints by treatment groups for double-blind period, and by treatment sequence for on-vatiquinone period.

Subject level listings of ECG and EEG will be provided.

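### In the double-blind safety summaries, the ECG baseline is the tracing taken 4 hours after the first dose, so the first-dose effect is subtracted from QTc change from baseline

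*SAP*

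**What the plan says.** SAP 3.5 contains two safety baseline rules. For the double-blind and open-label periods, baseline "will be defined as the last measurement prior to or on the date of first dose date". For the on-vatiquinone summaries, "the baseline will be defined as the last measurement prior to the first dose of vatiquinone". The first rule works by calendar date and admits any value from the dosing day. The second admits only values from before the dose.

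ECG comes under these rules. SAP 1.3.4 places it among the safety endpoints, under the heading "Physical Examination, Vital Signs, 12-lead Electrocardiogram (ECG) and Electroencephalogram (EEG"), and no section makes an exception for it. SAP 6.5 summarises "ECG results and change from baseline results (heart rate, PR interval, RR interval, QRS interval, QTc interval") by visit and assessment timepoint, by treatment group for the double-blind period and by treatment sequence for the on-vatiquinone period.

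On timing, footnote m of Table 2 in Protocol 7.1 states: "First dose for the placebo-controlled phase of the study will be taken the same day as the Baseline Visit". Protocol 7.1.2.1 says the same and lists the Baseline Visit tracing as "12-lead ECG at 4 hours postdose time-matched to pharmacokinetic (PK) blood collection". Footnote d applies this to every marked visit from Baseline on: "ECG measurement will be performed at 4 hours postdose during each visit, time-matched to PK blood collection". The schedule in SAP Appendix 1 gives the same timing. No pre-dose ECG is scheduled on Day 0. Apart from the Day 0 tracing, the only ECG before Week 24 is at Screening.

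**The concern.** A baseline should describe the untreated state. Under the date rule, a vatiquinone subject's ECG baseline is an on-drug tracing, and Protocol 7.3 describes the PK sampling times to which it is matched as lying near peak concentration. Week 24 change in that arm is then on-drug minus on-drug, while in the placebo arm it is drug-free minus drug-free. What is subtracted differs between the arms, so the comparison of changes does not remove it.

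The double-blind phase has only two scheduled ECGs after the first dose, Day 0 at 4 hours and Week 24. The whole randomised change-from-baseline analysis is therefore one contrast between them. A small mean QTc change in the vatiquinone arm could be read as reassuring when the rule itself could have produced it.

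Separate baselines for separate analysis periods are not an error in themselves. For a subject randomised to vatiquinone, however, both periods start with the same dose. By the text, that subject has the Day 0 tracing as baseline in one table and the Screening tracing in the other.

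**Working it through.** The plan states no ECG effect size or threshold, so there is no figure to reproduce. The check follows the rule through the schedule.

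**Which tracing is baseline**

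| ECG | Relation to first dose | Eligible under the double-blind rule? | Eligible under the on-vatiquinone rule (vatiquinone arm)? |
|---|---|---|---|
| Screening | Before | Yes | Yes |
| Day 0 | Same date, 4 hours after | Yes, and later than Screening, so it is chosen | No |
| Week 24 | After | No | No |

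**What the change then measures**

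Notation:
- B is the drug-free interval at Screening.
- d0 and d24 are shifts from Screening to Day 0 and to Week 24 that both arms share (time, food, hour of day).
- E1 is the drug effect 4 hours after the first dose, and Ess the effect 4 hours post-dose at Week 24. Both are zero on placebo.

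Double-blind rule in the SAP, with baseline B + d0 + E1 on vatiquinone and B + d0 on placebo:
- Day 0 change is 0 in both arms, because the tracing is subtracted from itself.
- Week 24 change on vatiquinone is (B + d24 + Ess) − (B + d0 + E1) = (d24 − d0) + (Ess − E1).
- Week 24 change on placebo is d24 − d0.
- The difference between arms is **Ess − E1**.

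Pre-dose rule, with the Screening baseline B in both arms:
- Day 0 change is d0 + E1 on vatiquinone and d0 on placebo, a difference of **E1**.
- Week 24 change is d24 + Ess on vatiquinone and d24 on placebo, a difference of **Ess**.

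The offset at Week 24 is exactly E1. This needs no assumption about the size of the effect.

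**Size, on assumed values**

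Let R = Ess/E1. The reported share of the Week 24 effect is (Ess − E1)/Ess = 1 − 1/R. The documents give neither E1 nor R. Taking E1 = 10 ms for illustration:

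| R | Ess (ms) | Reported at Week 24, Ess − E1 (ms) | Share reported | Share removed |
|---|---|---|---|---|
| 1 | 10 | 0 | 0% | 100% |
| 1.25 | 12.5 | 2.5 | 20% | 80% |
| 1.5 | 15 | 5 | 33% | 67% |
| 2 | 20 | 10 | 50% | 50% |

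The shares do not depend on E1; 5 ms or 20 ms gives the same percentages. If R is below 1, the reported difference has the opposite sign to the true effect.

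**The case against.** The strongest reply is that the effect is still visible elsewhere. SAP 6.5 summarises observed ECG values by arm and timepoint as well as changes, and provides subject listings. Randomisation balances the drug-free interval on average, so the between-arm difference in observed values estimates E1 at Day 0 and Ess at Week 24 whatever baseline is chosen. This stands. A reader might infer that the plan hides any acute ECG effect; the documents do not support that. What the observed values lack is the within-subject adjustment that a change score is meant to supply, with about 30 subjects per arm.

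Second, the on-vatiquinone text already uses a pre-dose baseline, so change in those summaries is not diminished. This stands too, and it means the Day 0 tracing is not treated as baseline throughout. But those summaries have no concurrent placebo comparison. In addition, SAP Table 2 labels the Day 0 visit Baseline for the vatiquinone/vatiquinone sequence, and SAP Section 6 summarises by nominal visit, so the text and the label pull apart for ECG.

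Third, only the first-dose part is removed. Any growth in effect with repeat dosing remains in the Week 24 change, and complete cancellation there requires R = 1, which nothing in the documents establishes.

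Fourth, the role of ECG is modest. Protocol 2.2.4 lists adverse events and laboratory variables as safety endpoints and does not name ECG. SAP Table 5 has no ECG criterion. No hypothesis test or dose-modification rule uses QTc. Protocol 1.4.1 reports no effect on ECG parameters in rat and dog and no potent hERG inhibition. These points lower the stakes. They do not make an on-drug baseline appropriate.

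**Conclusion.** The point holds as a defect in one set of descriptive tables. In the double-blind summaries of ECG change from baseline, the Day 0 change is zero by construction and the Week 24 difference between arms is short by E1. Those two statements follow from the rule and the schedule alone. Any figure in milliseconds or per cent rests on assumed values of E1 and R.

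Three wider readings are tempting and are not supported:
- That cardiac safety cannot be assessed in this trial. Observed values by arm and the on-vatiquinone changes remain available.
- That the same fault affects laboratory tests and vital signs. The documents do not place those post-dose on Day 0; the 4-hour timing is stated for ECG.
- That the open-label baseline is contaminated in the same way. SAP 3.7 puts the first open-label dose at home later on the Week 24 day, after the in-office double-blind dose, so a placebo subject's Week 24 tracing is still free of vatiquinone.

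Severity: should-fix. No efficacy conclusion or error rate depends on it.

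**What to change.** Make three changes to the SAP before the first database lock, by which time SAP Section 1 requires it to be final:

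1. In 3.5, for ECG in the double-blind period, define baseline as the last measurement before the first dose by date and clock time. Under the current schedule this is the Screening ECG.
2. In 6.5, report the Day 0 4-hour ECG as the first post-baseline timepoint, with its change from Screening by treatment group.
3. In Table 2, align the visit label for ECG with the on-vatiquinone definition, so that the Day 0 tracing is not labelled Baseline for the vatiquinone/vatiquinone sequence.

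No new data or procedures are needed. The cost is in the quality of the baseline. The Screening ECG is a single tracing that may be up to 42 days old, or older if diary training is extended, and it is not matched to the 4-hour fed timepoint used at Day 0 and Week 24. That adds some variance to the changes. The placebo arm takes care of any mean shift common to both arms, as the terms d0 and d24 show, but not of the extra variance. Keeping the observed values by arm beside the changes, as 6.5 already plans, lets the reader weigh this.

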3.6. Multiplicity Adjustment

To control the family-wise error rate for the primary and key secondary efficacy endpoints, a fixed sequence procedure will be used. Testing orders of the primary endpoint and the key secondary endpoints are listed as below:

- Primary endpoint: percentage change from baseline in the seizure frequency in motor seizures per 28 days during the double-blind period
- The first key secondary endpoint: number of disease-related hospitalization days

- The second key secondary endpoint: occurrence or recurrence of status epilepticus

The primary endpoint will be tested at the significance level of 0.05 (two-sided). If $p < 0.05$, then the primary endpoint will be considered statistically significant, and the study will be declared positive. If the test of the primary endpoint is statistically significant, then the key secondary endpoints will be tested in the order specified above, each at the 0.05 (two-sided) significance level. Only if the first key secondary endpoint is statistically significant at the 0.05 significance level, the second key secondary endpoint will be tested at the 0.05 significance level.

3.7. Missing Data Handling

In general, missing data will not be imputed, unless otherwise specified.

To minimize the impact from the missing data, the seizure frequency will be based on number of seizures on “valid days”. A “valid day” is defined as the day where seizure counts information is present.

In addition, a sensitivity analysis will be performed excluding all subjects with $< 80\%$ compliance in the seizure diary of valid days entered in the diary either during run-in period, or during double-blind period.

For analysis purposes, lab or PK values preceded by a “<” sign, ie, below the limits of quantification, will be considered as half of the limit of quantification. Lab or PK values preceded by a “>” sign, ie, above the limits of quantifications, will be considered as plus one unit of the minimum digit of the limit of quantifications. The original value will be included in the listing.

Per study design, last dose during double-blind period will be taken in the office the same day as first dose during open-label period, which will be taken at home later that day. When the dose time for first dose during open-label period is missing, all labs, vital signs taken on that day will be considered as prior to open-label period. All seizures, AE and concomitant medications that occurred on that day will be considered as occurred during the open-label period to be conservative, as all subjects will take vatiquinone during open-label period.

